16.0 Statistical Considerations and Methodology

16.1 Study Overview

This study will assess the confirmed response rate associated with Pembrolizumab (MK-3475) in small bowel adenocarcinoma. Additional endpoints consist of progression-free survival (PFS), overall survival (OS), and adverse events. Translational endpoints will be assessed as well using an exploratory analysis, given the small sample size.

16.2 Primary Endpoint

This study will assess the confirmed response rate associated with MK-3475/Pembrolizumab in small bowel adenocarcinoma. Confirmed response rate will be defined as meeting RECIST 1.1 criteria on two consecutive evaluations at least 4 weeks apart. Confirmed response will be evaluated using the first year of treatment (first 18 cycles of treatment). All patients meeting the eligibility criteria who have a signed consent form and have begun treatment will be evaluable for response.

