4.0 Test Schedule

Tests and procedures	Active Monitoring Phase			
	≤28 days prior to registration	Day 1 Cycle 1	Day 1 Cycles 2 -8 and beyond (+/-3 days)	End of treatment (PD, withdrawal, or removal ⁹) (+7days)
History and exam, wt, ECOG PS	X	X ^{6,8}	X ⁶	X
Height	X			
Adverse event assessment	X	X ⁸	X	X
Concomitant medication review	X	X ⁸	X	
Hematology: CBC/ differential	X	X	X	X
Chemistry: SGOT (AST), ALT, alk phos, T. bili, creatinine, calcium,, Na, K, glucose, LDH, bicarbonate, uric acid, Mg, Phosphorus, total protein, blood urea nitrogen, albumin	X	X	X	
PT/INR and aPTT	X			
Urinalysis ³	X			
T3, FT4 and TSH	X	X	X	
Tumor measurement (should include at least a CT of the abdomen/pelvis, and appropriate imaging of any other target site lesions) ^{1, 10}	X		X ⁵	X
CEA	X		X ⁷	X
Pregnancy test	X ²			
Mandatory blood sample (see Section 14.0) ⁸	X	X	X ⁴	X
Mandatory tissue sample (see Section 17.0)	X			

1. Use same imaging throughout the study.
2. For women of childbearing potential only. Must be done ≤7 days prior to registration.
3. Urine blood, glucose, protein, specific gravity. Microscopic exam if abnormalities on urinalysis results.
4. Collected cycles 2, 3, 4, 8 (see Section 14.0). Kits are required for this collection.
5. Every 4 cycles beginning with end of cycle 4, and at end of treatment.
6. Directed physical exam only.
7. Every even-numbered cycle, beginning with cycle 2, and at end of treatment.
8. ≤24 hours prior to treatment.
9. Continued study treatment beyond initial radiographic disease progression may be allowed; see Section 13.4 for details. These

patients would continue follow-up per test schedule until confirmed progression.

10. To be submitted <60 days after registration

R Research funded (see Section 19.0). Mandatory research blood draws should be collected and submitted *after* the patient is registered onto the study, but before beginning study treatment.

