7.0 Protocol Treatment

7.1 Treatment Schedule

Drug	Dose/Potency	Dose Frequency	Route of Administration	Regimen/Treatment Period	Use
Pembrolizumab	200 mg (flat dosing)	Q3W	IV infusion	Day 1 of each 3 week cycle	Experimental

Note: Trial treatment should begin ≤ 10 days after registration and as close as possible to the date on which treatment is allocated/assigned.

Note: Details on preparation and administration of pembrolizumab (MK-3475) are provided in section 15.0.

7.2 For this protocol, the patient must return to the consenting ACCRU institution for evaluation at least every 21 days (+/- 3 days) during treatment.

7.3 Dosing interruptions, not due to adverse effects.

Dosing interruptions are permitted in the case of medical / surgical events or logistical reasons not related to study therapy (e.g., elective surgery, unrelated medical events, patient vacation, and/or holidays). Subjects should be placed back on study therapy within 3 weeks of the scheduled interruption. The reason for interruption should be documented in the patient's study record.

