8.0 Dosage Modification Based on Adverse Events

8.1 Dose Levels

No dose level adjustments are recommended for any adverse reaction, but the dosing interval may be increased by 1 week if required.

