attenuation corrected image; otherwise, an FDG-PET scanned lesion is considered ‘negative.’ New lesions on the basis of FDG-PET imaging can be identified according to the following algorithm:

- a. Negative FDG-PET at baseline with a positive FDG-PET at follow-up is a sign of PD based on a new lesion.
- b. No FDG-PET at baseline and a positive FDG-PET at follow-up:
 - i. If the positive FDG-PET at follow-up corresponds to a new site of disease confirmed by CT, this is PD.
 - ii. If the positive FDG-PET at follow-up is not confirmed as a new site of disease on CT at the same evaluation, additional follow-up CT scans (i.e., additional follow-up scans at least 4 weeks later) are needed to determine if there is truly progression occurring at that site. In this situation, the date of PD will be the date of the initial abnormal FDG-PET scan.
 - iii. If the positive FDG-PET at follow-up corresponds to a pre-existing site of disease on CT that is not progressing on the basis of the anatomic images, it is not classified as PD.

11.33 Measurement at Follow-up Evaluation:

- A subsequent scan must be obtained at least four weeks following initial documentation of an objective status of either complete response (CR) or partial response (PR).
- In the case of stable disease (SD), follow-up measurements must have met the SD criteria at least once after study entry at a minimum interval of 6 weeks (see Section 11.44).
- The cytological confirmation of the neoplastic origin of any effusion that appears or worsens during treatment when the measurable tumor has met criteria for response or stable disease is mandatory to differentiate between response or stable disease (an effusion may be a side effect of the treatment) and progressive disease.
- Cytologic and histologic techniques can be used to differentiate between PR and CR in rare cases (e.g., residual lesions in tumor types such as germ cell tumors, where known residual benign tumors can remain.)

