13.5 Subject Withdrawal/Discontinuation Criteria

Subjects may withdraw consent at any time for any reason or be dropped from the trial at the discretion of the investigator should any untoward effect occur. In addition, a subject may be withdrawn by the investigator or the Sponsor if enrollment into the trial is inappropriate, the trial plan is violated, or for administrative and/or other safety reasons. .

A subject must be discontinued from the trial for any of the following reasons:

- The subject or legal representative (such as a parent or legal guardian) withdraws consent.
- Confirmed radiographic disease progression (but remain on trial for long term survival)
- Unacceptable adverse experiences
- Intercurrent illness that prevents further administration of treatment
- Investigator's decision to withdraw the subject
- The subject has a confirmed positive serum pregnancy test
- Noncompliance with trial treatment or procedure requirements
- The subject is lost to follow-up
- Completed 24 months of uninterrupted treatment with pembrolizumab or 35 administrations of study medication, whichever is later.

Note: 24 months of study medication is calculated from the date of first dose. Subjects who stop pembrolizumab after 24 months may be eligible for up to one year of additional study treatment if they progress after stopping study treatment. To permit continued study treatment beyond initial radiographic disease progression, see section 7.6 Treatment Continuation.

Administrative reasons

Subjects who discontinue trial treatment for any reason will move into the event-monitoring phase and should be assessed every 3 months until progression and every 6 months after progression for a maximum follow-up time of 5 years from study entry.

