16.5 Accrual time and Study Duration

The anticipated accrual rate is approximately 3 patients per month. Therefore, the accrual period for this phase II study is expected to be approximately 14 months, if the study goes to full accrual. The final analysis can begin approximately 30 months after the trial begins, i.e. as soon as the last patient has been monitored for 12 months plus data clean-up and analysis.

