The primary endpoint is the confirmed response rate, evaluated over the first year of treatment. The final analysis is expected to take place around 30 months after the study begins, so we expect that the primary endpoint completion time to be around 30 months after study activation.

16.9d Inclusion of Women and Minorities

This study will be available to all eligible patients, regardless of race, gender, or ethnic origin. There is no information currently available regarding differential effects of this regimen in subsets defined by race, gender, or ethnicity, and there is no reason to expect such differences to exist. Based on prior studies involving similar disease sites, we expect about 10% of patients will be classified as minorities by race and about 30% of patients to be women. Expected sizes of racial by gender subsets are shown in the following table:

Accrual Targets			
Ethnic Category	Sex/Gender		
	Females	Males	Total
Hispanic or Latino	0	0	0
Not Hispanic or Latino	13	28	41
Ethnic Category: Total of all subjects	13	28	41
Racial Category			

Ethnic Category	Accrual Targets		
	Sex/Gender		
	Females	Males	Total
American Indian or Alaskan Native	1	0	1
Asian	0	1	1
Black or African American	0	1	1
Native Hawaiian or other Pacific Islander	0	1	1
White	11	25	36
Racial Category: Total of all subjects	13	28	41

Ethnic Categories: **Hispanic or Latino** – a person of Cuban, Mexican, Puerto Rican, South or Central American, or other Spanish culture or origin, regardless of race. The term “Spanish origin” can also be used in addition to “Hispanic or Latino.”

Not Hispanic or Latino

Racial Categories: **American Indian or Alaskan Native** – a person having origins in any of the original peoples of North, Central, or South America, and who maintains tribal affiliations or community attachment.

Asian – a person having origins in any of the original peoples of the Far East, Southeast Asia, or the Indian subcontinent including, for example, Cambodia, China, India, Japan, Korea, Malaysia, Pakistan, the Philippine Islands, Thailand, and Vietnam. (Note: Individuals from the Philippine Islands have been recorded as Pacific Islanders in previous data collection strategies.)

Black or African American – a person having origins in any of the black racial groups of Africa. Terms such as “Haitian” or “Negro” can be used in addition to “Black or African American.”

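### Does it matter that 16.2 ends the response window both at one year and at 18 cycles?

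*Combined protocol and SAP*

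**What the plan says.** Section 16.2 defines a confirmed response as RECIST 1.1 response at two consecutive evaluations at least 4 weeks apart, and adds: "Confirmed response will be evaluated using the first year of treatment (first 18 cycles of treatment"). Two other places restate the period without cycles. Section 16.9c says "The primary endpoint is the confirmed response rate, evaluated over the first year of treatment", and 16.5 times the final analysis "as soon as the last patient has been monitored for 12 months plus data clean-up and analysis".

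The rest of the timetable comes from elsewhere:

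- The Schema gives a 21-day cycle.
- Scans are due, in footnote 5 of Section 4.0, "Every 4 cycles beginning with end of cycle 4, and at end of treatment". Section 11.1 describes the same schedule as 12-weekly, equating that with 4 cycles.
- On confirmation, 11.33 says "A subsequent scan must be obtained at least four weeks following initial documentation of an objective status of either complete response (CR") or PR. It sets a minimum and no maximum.
- Dosing can slip. Under 8.1 "the dosing interval may be increased by 1 week if required", and under 7.3 "Subjects should be placed back on study therapy within 3 weeks of the scheduled interruption".

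Section 13.5 also pairs a calendar limit with a dose count, but it ranks them: "Completed 24 months of uninterrupted treatment with pembrolizumab or 35 administrations of study medication, whichever is later". Section 16.2 has no such rule.

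**The concern.** One endpoint seems to have two definitions. A year ends on day 365; 18 cycles end on day 378, or later if delayed cycles are counted as given. A patient whose response is confirmed between those dates is a responder on one reading and not on the other.

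The decision rule in 16.32 is a hard cut: 6 or fewer confirmed responses in 35 means insufficient activity, 7 or more means success. One reclassified patient could reverse the conclusion. If the window were settled only after the count was known, whoever settled it could favour one result. Because 13.5 ranks its two clocks, the silence in 16.2 looks like an oversight.

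**Working it through.** **The plan's own figures.** With 35 patients and success at 7 or more, P(X ≥ 7) is 0.0552 at a true rate of 10% and 0.9350 at 30%. These reproduce the stated 0.06 and 94%. Neither depends on the window's length, provided the 10% and 30% are read as rates over whichever window is used.

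**The two ends.** 18 × 21 = 378 days; 378 − 365 = 13 days.

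**Scans without delay** (days from first dose; scan k at 84k days, earliest confirmation 28 days later):

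| Scan | Day | Earliest confirmation | Next routine scan |
|---|---|---|---|
| 1 | 84 | 112 | 168 |
| 2 | 168 | 196 | 252 |
| 3 | 252 | 280 | 336 |
| 4 | 336 | 364 | 420 |

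Responses first seen at scans 1 to 3 count on both readings, even if confirmed only at the next routine scan. A fourth-scan response confirmed on day 364 or 365 also counts on both. Confirmed on day 420, it counts on neither. Only confirmation on days 366 to 378 separates the two.

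**With delay.** Suppose scans move with cycles and delayed cycles are counted as given. After a cumulative delay of D days, the earliest fourth-scan confirmation is day 364 + D and cycle 18 ends on day 378 + D.

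- From D = 2, a fourth-scan response cannot be confirmed by day 365 but can be within 18 cycles.
- With two 3-week interruptions (D = 42), scans 3 and 4 fall on days 294 and 378 and cycle 18 ends on day 420. A third-scan response confirmed at the next routine scan then counts on cycles only. Rescanned after four weeks (294 + 28 = 322), it counts on both.
- If scans keep to 12-week dates, as 11.1 can be read, delay does not move them and scan 4 stays on day 336.
- If only the first observation must fall inside the window, the fourth scan passes day 365 only once D exceeds 365 − 336 = 29 days.

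**Why 18?** Dose 18 falls on day 17 × 21 = 357 and dose 19 on day 378, so 18 is the number of cycles that start within a year. The 35 administrations in 13.5 fit the same count: dose 35 is on day 714 and dose 36 on day 735, against 730 days in 24 months. The parenthesis reads naturally as a gloss on the year.

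**Size.** The documents do not say how many responders are seen this late. As an assumption only, let the 18-cycle window add 2%, 5% or 10% to the responders counted in a year. P(X ≥ 7) for n = 35 becomes:

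| One-year rate | No addition | +2% | +5% | +10% |
|---|---|---|---|---|
| 10% | 5.5% | 6.0% | 6.8% | 8.3% |
| 20% | 56.7% | 59.0% | 62.4% | 67.7% |
| 30% | 93.5% | 94.4% | 95.5% | 97.0% |

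The largest change, 11.0 points, needs both the largest assumed share and a true rate of 20%, between the two design rates.

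**Timing.** At 30.44 days per month, 378 days is 12.4 months. With the 14-month accrual of 16.5 the last patient's window closes at month 26.4; with the 17 months in Section 1.0, at month 29.4. Both precede the month-30 analysis.

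**The case for a change.** The best case for a change is that the ambiguity sits in the endpoint definition itself. The year leaves one day to confirm a fourth-scan response (365 − 364), against 14 days on the cycle count. The ordinary 3-day dosing window can use up that one day. Exactly 6 responders in 35, where one added late responder would reverse the conclusion, has probability 7.6%, 16.1% and 3.8% at true rates of 10%, 20% and 30%. Naming one end would take a sentence or two.

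The arithmetic stands, and so does the absence of a ranking. Three parts of the argument are weaker.

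- The boundary probabilities apply only if a response also falls in the disputed days, and the plan gives no reason to expect many first responses at about month 11.
- It is not established that the cycle count can only add responders. Take a patient who stops after cycle 8 with a first PR and is confirmed off treatment before day 365. That patient counts on the calendar year but may not if only cycles actually given are counted. The ambiguity therefore does not push in one direction on every reading, and the tabulated differences are chances of opposite conclusions only where the longer window never loses a responder.
- Fixing the window would not by itself secure the late confirmations. Because 11.33 sets no upper limit, a rescan at day 420 complies with it. Making fourth-scan responses count would mean asking for an additional scan.

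**Conclusion.** The two window ends in 16.2 do differ, by 13 days without delay and by more if delayed cycles are counted as given. This is loose wording rather than a fault in the design. The two other statements of the period, in 16.5 and 16.9c, use 12 months or the first year, and 18 is the number of cycles that start in a year, so the calendar year is the sensible reading for an analyst to apply. Whether the confirming scan must also fall inside it is a choice that competent statisticians could make either way.

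On the planned schedule the readings part only for a fourth-scan response confirmed on days 366 to 378. The wider differences depend on dosing delays moving the scans, which 11.1 leaves open. The effect on the 7-of-35 decision is probably small; the documents do not allow it to be measured, and the 2% to 10% shares above are assumptions. The stated significance level and power stand, and either window gives a valid test if applied without regard to the count. No change to the plan is needed.

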16.3 Study Design for Primary Endpoint

16.31 Ho vs. Ha Hypothesis for the Primary Endpoint

To evaluate the confirmed response rate we will be using a 1-stage design to test the hypothesis of the treatment being ineffective ($H_0: p < 10\%$) vs. the hypothesis of the treatment being clinically effective ($H_a: p > 30\%$).

16.32 Final Analysis Decision Rule

Enter a total of 35 evaluable patients. If 6 or fewer of these 35 patients have a confirmed response, we will conclude that this treatment is insufficiently active in this population. If 7 or more of these 35 patients have a confirmed response (20%), this will be considered adequate evidence of efficacy of this treatment and may be recommended for further testing in subsequent studies.

16.33 Sample Size and Power

We anticipate accruing an additional 5 patients to account for ineligibilities, cancellations, major violations, or other reasons. Therefore, maximum accrual is 41 patients. This design has a significance level of 0.06 when the confirmed response rate is 10%, and 94% power to detect a confirmed response rate of 30%.

16.4 Total Sample Size

35 evaluable patients will be enrolled, if the study reaches full accrual. We anticipate accruing an additional 5 patients to account for ineligibility's, cancellations, major violations, or other reasons. Therefore, maximum accrual is 41 patients.

16.5 Accrual time and Study Duration

The anticipated accrual rate is approximately 3 patients per month. Therefore, the accrual period for this phase II study is expected to be approximately 14 months, if the study goes to full accrual. The final analysis can begin approximately 30 months after the trial begins, i.e. as soon as the last patient has been monitored for 12 months plus data clean-up and analysis.

16.6 Secondary endpoints

These endpoints include progression-free survival (PFS), overall survival (OS), and adverse events.

- Progression-free survival (PFS) is defined as the time from study entry to the first of either disease progression or death from any cause, where disease progression will be determined based on RECIST 1.1 criteria. PFS will be estimated using the Kaplan-Meier method.
- Overall survival (OS) is defined as the time from study entry to death from any cause. OS will be estimated using the Kaplan-Meier method.
- Adverse events: The maximum grade for each type of adverse event will be summarized using CTCAE version 4.03. The frequency and percentage of grade 3+ adverse events will be summarized.

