2.2 Secondary Objectives and Endpoints

- 2.21 To assess survival endpoints (OS, PFS), including stratified analysis by tumor site.
- 2.22 To assess whether pembrolizumab is safe in SBA patients by assessing adverse events.

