10.52 Baseline and Adverse Events Evaluations

Pre-treatment symptoms/conditions to be graded at baseline and adverse events to be graded at each evaluation per the CTCAE v4.03 grading unless otherwise stated in the table below:

System Organ Class (SOC)	CTC Adverse Event Term (CTCAE v.4.03)	Baseline	At each evaluation
Investigations	Aspartate aminotransferase (AST) increased	X	X
	Alanine aminotransferase (ALT) increased	X	X
	Blood bilirubin increased	X	X
	Alkaline phosphatase increased	X	X
Endocrine Disorders	Hyperthyroidism	X	X
	Hypothyroidism	X	X
	Other: Specify hypophysitis	X	X

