10.53 Case Report Forms - Academic and Community Cancer Research United (ACCRU)

Submit the following AEs not specified in Section 10.5 (paper or electronic, as applicable)

10.531 Grade 2 AEs deemed *possibly, probably, or definitely* related to the study treatment or procedure.

10.532 Grade 3 and 4 AEs regardless of attribution to the study treatment or procedure.

10.533 Grade 5 AEs (Deaths)

10.5331 Any death within 30 days of the patient's last study treatment or procedure regardless of attribution to the study treatment or procedure.

10.5332 Any death more than 30 days after the patient's last study treatment or procedure that is felt to be at least possibly treatment related must also be submitted as a Grade 5 AE, with a CTCAE type and attribution assigned.

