Metabolism – Pembrolizumab is catabolized through non-specific pathways; metabolism does not contribute to its CL.

15.16 **Potential Drug Interactions:** There are no known significant drug interactions.

15.17 **Known potential toxicities:**

Very common known potential toxicities, $\geq 10\%$:
Gastrointestinal disorders; diarrhea, nausea, abdominal pain
Skin and subcutaneous tissue disorders; rash, pruritis
General disorders and administration site conditions: fatigue

Common known potential toxicities, $\geq 1\% \leq 10\%$:

Blood and lymphatic system disorders; anemia
Immune system disorders: infusion related reaction
Endocrine disorders: hyperthyroidism, hypothyroidism
Metabolism and nutrition disorders: decreased appetite
Nervous system disorders: headache, dizziness, dysgeusia
Respiratory, thoracic, and mediastinal disorders: pneumonitis, dyspnea, cough
Gastrointestinal disorders: colitis, vomiting, constipation, dry mouth
Skin and subcutaneous tissue disorders: severe skin reactions, vitiligo, dry skin, erythema
Musculoskeletal and connective tissue disorders: arthralgia, myositis, musculoskeletal pain, pain in extremity
General disorders and administration site conditions: asthenia, edema, pyrexia, influenza like illness, chills
Investigations: alanine aminotransferase increased, aspartate aminotransferase increased, blood alkaline phosphatase increased, blood creatinine increased

Uncommon known potential toxicities, $\geq 0.1\% - 1\%$:

Infusion related reactions:
Blood and lymphatic system disorders: neutropenia, thrombocytopenia, leukopenia, lymphopenia, eosinophilia
Endocrine disorders: hypophysitis, adrenal insufficiency, thyroiditis, hypopituitarism
Metabolism and nutrition disorders: type I diabetes mellitus, hyponatremia, hypokalemia, hypocalcemia
Psychiatric disorders: insomnia, confusional state
Nervous system disorders: epilepsy, lethargy, peripheral neuropathy
Eye disorders: uveitis, dry eye
Cardiac disorders: myocarditis, atrial fibrillation
Vascular disorders: hypertension
Gastrointestinal disorders: pancreatitis
Hepatobiliary disorders: hepatitis
Skin and subcutaneous tissue disorders: lichenoid keratosis, psoriasis, alopecia, dermatitis, dermatitis acneiform, eczema, hair color changes, papule

Musculoskeletal and connective tissue disorders: tenosynovitis
Renal and urinary disorders: nephritis, acute kidney injury
Investigations: blood bilirubin increased, amylase increased, hypercalcemia

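### Section 16.6 summarizes maximum grade for every adverse-event type without a grade or attribution limit, but for terms outside the seven in 10.52 the CRF rule in 10.53 does not ask for grade 1 or unrelated grade 2 events

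*Combined protocol and SAP*

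**What the plan says.** The safety objective in section 2.2 is "To assess whether pembrolizumab is safe in SBA patients by assessing adverse events". Section 16.6 turns it into two summaries. The first is "The maximum grade for each type of adverse event will be summarized using CTCAE version 4.03", with no restriction by grade or attribution. The second is "The frequency and percentage of grade 3+ adverse events will be summarized".

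What reaches the database is set in section 10.5. Section 10.52 asks for "Pre-treatment symptoms/conditions to be graded at baseline and adverse events to be graded at each evaluation per the CTCAE v4.03 grading unless otherwise stated" in its table. That table has seven terms: AST, ALT, bilirubin and alkaline phosphatase increases, hyperthyroidism, hypothyroidism and hypophysitis.

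Section 10.53 covers the rest and opens "Submit the following AEs not specified in Section 10.5 (paper or electronic, as applicable". Since 10.53 itself lies inside 10.5, I take this to mean terms not in the 10.52 table. It then lists three groups:
- grade 2 events at least possibly related (10.531);
- "Grade 3 and 4 AEs regardless of attribution to the study treatment or procedure" (10.532);
- grade 5 events, meaning deaths within 30 days of last treatment, or later if at least possibly related (10.533).

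Section 15.17 names six toxicities expected in 10% or more of patients: "Gastrointestinal disorders; diarrhea, nausea, abdominal pain", together with rash, pruritus and fatigue. None of the six is in the 10.52 table.

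**The concern.** The endpoint and the data capture do not match. A patient whose worst rash is grade 1, or whose worst fatigue is grade 2 and judged unrelated, has a maximum grade that 16.6 intends to summarize but 10.53 does not ask the site to submit. Nothing in 16.6 limits the summary to collected events or says how uncollected grades are to be shown.

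Two consequences follow if both sections are applied as written. Ascertainment is complete for seven terms and truncated for the others, so frequencies below grade 3 cannot be compared across terms. Within an unsolicited term, the attribution rule also changes between grade 2 (related only) and grade 3 (any attribution), so adjacent grade columns count different things.

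The truncated group includes all the toxicities that the protocol expects to be most frequent. Section 16.7 also plans to correlate adverse events with translational markers without naming a grade threshold. Any low-grade variable used there would carry the same gap.

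**Working it through.** The plan states no figure on this point, so the main check is a comparison of the rules.

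**Step 1. Collection rules side by side**

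| Event | Seven terms in 10.52 | Any other term under 10.53 |
|---|---|---|
| Grade 1 | graded at each evaluation | not requested |
| Grade 2, at least possibly related | graded at each evaluation | requested |
| Grade 2, unlikely or unrelated | graded at each evaluation | not requested |
| Grade 3-4, any attribution | graded at each evaluation | requested |

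Grade 5 follows 10.533 and is not at issue. Section 16.6 needs every row for every term, and two rows are missing outside the seven.

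**Step 2. Other routes into the data**
- 10.1 g sends every expedited event into the routine data. Under 10.41 this includes grade 1-2 events with hospitalization of 24 hours or more.
- 10.3352 puts all events associated with an overdose on the Adverse Event CRF, with no grade limit.
- 10.31 lists events, mostly at grade 1-2 (enterocolitis, pneumonitis, dyspnea, cough, nephritis and others), that are exempt from expedited reporting but still go to routine reporting. Its heading concerns expected serious events and it refers back to 10.5, so it is unclear whether it widens 10.53. It names none of the six very common toxicities.

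These routes narrow the gap but do not close it for ordinary grade 1 diarrhea, nausea, abdominal pain, rash, pruritus or fatigue.

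**Step 3. Expected frequencies in 15.17**
- Six unsolicited terms: 10% or more.
- AST, ALT, alkaline phosphatase, hyperthyroidism, hypothyroidism (solicited): 1% to 10%.
- Bilirubin, hypophysitis (solicited): 0.1% to 1%.

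**Step 4. Illustration of size (assumed inputs)**

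Let N be 35 (evaluable target) to 41 (maximum accrual), p the true any-grade rate of at least possibly related events, and s the share of affected patients whose worst grade is 1. Section 15.17 gives only the 10% floor. The values of p above 10% and all values of s are assumptions.

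Patients without a record = N × p × s. Rate shown = p × (1 − s).

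| p | s | Without a record, N = 35 to 41 | Rate shown |
|---|---|---|---|
| 10% | 25% | 0.9 to 1.0 | 7.5% |
| 10% | 75% | 2.6 to 3.1 | 2.5% |
| 30% | 25% | 2.6 to 3.1 | 22.5% |
| 30% | 75% | 7.9 to 9.2 | 7.5% |

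For example, 41 × 0.30 × 0.75 = 9.2 patients, and 30% × 0.25 = 7.5%. Unrelated grade 2 events would add to the loss.

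**Step 5. What is not affected**

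The grade 3+ summary uses grades collected regardless of attribution. The stopping rule in 16.9a uses grade 4 non-hematologic and grade 5 events at least possibly related, all of which are collected. The primary endpoint does not use adverse events.

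**The case against.** The strongest reply is that 10.53 states its collection rule openly, that reduced collection of low-grade events may be deliberate, and that a maximum grade over submitted events, labelled as such, would satisfy 16.6. The endpoint is descriptive, in a single-arm trial of at most 41 patients, and no decision depends on its low-grade part. This largely stands as a limit on importance. It justifies 10.53, but it does not justify leaving 16.6 unrestricted, because the label is not in the plan.

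Three stronger readings are tempting, and the documents do not support them:
- *Low-grade events are collected only for the seven terms.* Related grade 2 events are collected for every term, and 10.1 g, 10.3352 and possibly 10.31 bring in more.
- *Patients with low-grade toxicity will be tabulated as having none.* Section 16.6 specifies neither such a category nor an any-grade column. This would be a consequence of table layout, and labelling would prevent it.
- *Liver and thyroid events will look more common than rash, fatigue or diarrhea.* In step 4, a true 10% rate shrinks into the 1% to 10% band of the thyroid and AST/ALT terms. A true 30% rate stays above that band at s = 25% and falls into it at s = 75%. A reversed order is possible but not established.

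**Conclusion.** The mismatch holds. For terms outside the 10.52 table, the maximum grade that 16.6 describes cannot be derived below related grade 2, apart from events entering by the routes in step 2. This covers all six toxicities that 15.17 places at 10% or more. Maximum grade and any-grade frequency for those terms are truncated and should not be set beside the seven solicited terms.

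The documents do not give the size. The illustration of about 1 to 9 patients per term without a record depends wholly on the assumed rate and grade-1 share. The effect is confined to the low-grade part of a descriptive secondary endpoint. It is worth correcting because two stated rules conflict and the correction is small.

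**What to change.** In 16.6, state that maximum grade is summarized at all grades only for the 10.52 terms. For all other terms, report in separate columns (a) grade 2 or higher, at least possibly related, and (b) grade 3 or higher regardless of attribution. Give no any-grade total and no no-event category for these terms. State in 10.31 or 10.53 whether the grade 1-2 events listed in 10.31 are to be submitted when they are not serious. Any low-grade variable used under 16.7 should follow the same limits.

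This needs a few sentences and no new data. The downside is a narrower safety table.

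Optionally, for patients not yet treated, add the six very common 15.17 terms to the 10.52 table. Section 4.0 already schedules an adverse-event assessment at each cycle, so the cost is a few CRF lines per visit. This is secondary: activation is dated February 2017 and the current addendum September 2019, against about 14 months of planned accrual. The documents do not give accrual status, but added terms would not be prospectively solicited in patients already treated, so the two groups would have to be reported separately.
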